8.3.8. Other Safety Data

None.

8.3.9. Concomitant Treatments

All concomitant medication(s) as well as non-drug treatment(s) will be provided in the listings.

8.3.10. Screening and Other Special Purpose Data

Prior concomitant medications for cancer therapy, response to regimen, prior radiation treatment and prior anti-cancer surgery collected at screening will be provided in the listings.

10. APPENDIX

Appendix 1. Time to Event Data Analysis Censoring Rules

Table 3. Progression Free Survival and Duration of Response

Situation	Date of Progression/Censoring¹	Outcome
Inadequate baseline assessment	First dosing date in Cycle 1	Censored
No on-study assessments	First dosing date in Cycle 1	Censored
Alive, on treatment ² and no Progression	Date of last objective tumor assessment	Censored
Progression Documented on or between scheduled tumor assessments prior to treatment discontinuation ²	Date of first objective tumor assessment showing objective progression	Progressed (Event)
Treatment discontinuation for undocumented progression	Date of last objective tumor assessment prior to discontinuation ²	Censored
Treatment discontinuation due to toxicity or other reason	Date of last objective tumor assessment prior to discontinuation ²	Censored
Death prior to first planned tumor assessment	Date of death	Death (Event)
Death without objective progression prior to treatment discontinuation ²	Date of death	Death (Event)
Death or progression after 2 or more missed tumor assessments	Date of last objective tumor assessment prior to the event	Censored

1: For date of censorship, if a tumor assessment takes place over a number of days (eg, superficial lesions one day, scans another), the last date is used as the assessment date.

2: or within 28 days of discontinuation of treatment.

Table 4. Time to Progression

Situation	Date of Progression/Censoring¹	Outcome
Inadequate baseline assessment	First dosing date in Cycle 1	Censored
No on-study assessments	First dosing date in Cycle 1	Censored
Alive, on treatment ² and no Progression	Date of last objective tumor assessment	Censored
Progression Documented on or between scheduled tumor assessments prior to treatment discontinuation ²	Date of first objective tumor assessment showing objective progression	Progressed (Event)
Treatment discontinuation for undocumented progression	Date of last objective tumor assessment prior to discontinuation ²	Censored

Treatment discontinuation due to toxicity or other reason	Date of last objective tumor assessment prior to discontinuation ²	Censored
New anticancer treatment <28 days after discontinuation of treatment without progression	Date of last objective tumor assessment prior to new anticancer treatment	Censored
Death prior to first planned tumor assessment	Start date (C1D1)	Censored
Death without objective progression prior to treatment discontinuation ²	Date of last objective tumor assessment prior to death	Censored
Progression after 2 or more missed tumor assessments	Date of last objective tumor assessment prior to the event	Censored

1: For censoring date, if a tumor assessment takes place over a number of days (eg, superficial lesions one day, scans another), the last date is used as the assessment date.

2: or within 28 days of discontinuation of treatment.

DOSD and DOR

Censoring rules for DOSD and DOR will be the same as for PFS.

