6. ENDPOINTS AND COVARIATES

6.1. Efficacy Endpoint(s)

CCI

The main

analysis populations will be based on mITT and EP (see Section Analysis Sets).

Disease response will be presented in the form of patient data listings that include, but are not limited to starting dose, disease response at each visit, and best overall response. In addition, progression date, death date, date of first response and last disease assessment date, and date of last contact will be listed.

Summary of objective response rates will be provided by descriptive statistics. Objective tumor response, as assessed using the Response Evaluation Criteria in Solid Tumor (RECIST) version 1.1 by calculating the Objective Response Rate (ORR) and Progression-Free Survival (PFS).

Progression-free survival (PFS) is the time from start date to date of first documentation of progression, or death due to any cause. Progression is defined as the appearance of local, regional or distant disease of the same type after complete response or progression of pre-existing lesions. It does not include second primary malignancies of unrelated types.

Overall survival (OS) is the time from start date to date of death due to any cause.

Duration of Response (DOR) is defined as the duration of overall response measured from the time measurement criteria are met for complete response (CR) or partial response (PR) (whichever is first recorded) until the first date that recurrent or progressive disease is objectively documented (taking as reference for progressive disease the smallest measurements recorded since the treatment started).

Duration of Stable Disease (DOSD) is defined as stable disease measured from the start of the treatment until the criteria for progression are met, taking as reference the smallest measurements recorded since the treatment started, including the baseline measurements.

For tumor response data, the following analyses may be performed:

1. Tumor response (CR, PR, SD, PD, etc.) by cohort and visit, separately for RECIST 1.1 and irRECIST. Investigator provided tumor response will be presented by descriptive statistics (frequency and percentage).

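### SAP Table 3 has overlapping rows and no order of precedence, so a death in a participant with no on-study scan or an inadequate baseline can be read as a PFS event or as a Day 1 censoring

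*SAP*

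**What the plan says.** SAP 6.1 states that PFS "is the time from start date to date of first documentation of progression, or death due to any cause". It sets time zero at the first vaccination on Cycle 1 Day 1 and, for a Kaplan-Meier analysis, takes the event as progression or death, whichever is earlier.

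SAP Appendix 1, Table 3 gives the censoring rules for PFS and duration of response. Counting rows from the top:

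- Row 1, "Inadequate baseline assessment", and row 2, "No on-study assessments": censored at the first dosing date in Cycle 1.
- Row 3: limited to participants who are alive, on treatment and with "no Progression"; censored at the last tumor assessment.
- Row 7, "Death prior to first planned tumor assessment": event on the date of death.
- Row 8, "Death without objective progression prior to treatment discontinuation", extended by footnote 2 to 28 days after discontinuation: event on the date of death.
- Row 9, "Death or progression after 2 or more missed tumor assessments": censored at the last assessment before the event.

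A sentence after Table 4 applies the PFS rules to duration of stable disease (DOSD) and duration of response as well. No text or footnote gives an order of precedence among the rows.

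**The concern.** Row 3 shows that the table can condition on vital status when it means to. Rows 1 and 2 do not. A participant who dies before any follow-up scan, or who dies with an inadequate baseline, therefore fits a row that censors at zero follow-up and also a row that counts the death.

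Knowing that someone died needs neither a baseline nor a follow-up scan. If a programmer applies rows 1 and 2 first, the deaths removed are mostly the earliest ones. What remains estimates PFS among people who lived long enough to be scanned, and it errs in the regimen's favour. If the order is settled only at the analysis of an open-label study, it is settled with the outcomes known.

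**Working it through.** **Inputs.** Table 3 and footnote 2 (SAP Appendix 1); the PFS definition and time zero (SAP 6.1); first on-study scan 8 weeks after Cycle 1 Day 1, then every 8 weeks up to Week 32 (protocol Schedule of Activities, tumor assessment footnote); about 36 participants in Part 1 (SAP 2.1); about 30 in Part 2 (protocol 9.3). Neither document gives a PFS sample size, event count or early-death rate, so there is no figure of the plan to reproduce.

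**Step 1: which rows does each death meet?**

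| Situation | Rows 1–2 | Rows 7–8 | Row 9 |
|---|---|---|---|
| No on-study scan, death before Week 8 | Censored Day 1 (row 2) | Event (row 7) | Not met |
| No on-study scan, only Week 8 missed, death on treatment or within 28 days of stopping | Censored Day 1 (row 2) | Event (row 8) | Not met |
| No on-study scan, two or more missed, death on treatment | Censored Day 1 (row 2) | Event if row 8 is read alone | Censored |
| Inadequate baseline, death before Week 8 | Censored Day 1 (row 1) | Event (row 7) | Not met |
| Inadequate baseline, scans kept up, death on treatment without progression | Censored Day 1 (row 1) | Event (row 8) | Not met |

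Lines 1, 2, 4 and 5 are direct conflicts between the first two rows and the death rows. In line 3, rows 2 and 9 agree that the outcome is censored. A death more than 28 days after discontinuation and after the first planned scan meets neither event row and lies outside this point.

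The row 1 overlap has no time limit: read literally, it removes a death at any time on treatment. It can also arise without a protocol breach. The protocol allows screening images up to 5 weeks before registration, while Appendix 3 of both documents calls a baseline adequate only if scans fall within 28 days before treatment.

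**Step 2: size for deaths before any scan.** Let d of n participants die before Week 8 without a scan, and suppose nothing else happens before Week 8. Just before the first scan:

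- deaths as events: S = 1 − d/n
- deaths censored at time zero: S = 1, with a risk set of n − d

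Part 1, n = 36, d assumed:

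- d = 1: 1 − 1/36 = 97.2%
- d = 2: 1 − 2/36 = 94.4%
- d = 4: 1 − 4/36 = 88.9%
- d = 6: 1 − 6/36 = 83.3%

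Each compares with 100% under Day 1 censoring.

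If the table were carried into Part 2, n = 30, d assumed:

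- d = 2: 1 − 2/30 = 93.3%
- d = 3: 1 − 3/30 = 90.0%
- d = 5: 1 − 5/30 = 83.3%

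The gap to 100% is 7 to 17 points.

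**Step 3: effect on the median.** Assume exponential PFS with a median of 4 months in the other participants, so λ = ln 2 / 4. With deaths as events and n = 36, the overall median is ln[(1 − d/n)/0.5]/λ. This is 3.84 months for d = 1 and 2.95 months for d = 6, against 4.0 months under Day 1 censoring.

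**The case against.** The strongest reply is that the specific death rows plainly govern. If row 2 overrode row 7, row 7 would be almost empty, because someone who dies before the first planned scan has no scan unless an unscheduled one was done. The PFS definition and the Kaplan-Meier event definition in SAP 6.1 both include death. Table 4, for time to progression, lists the same early deaths and censors them at the start date. Table 3 gives them the opposite outcome, and that difference looks deliberate.

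This argument stands for row 7. A reader might infer from rows 1 and 2 that the plan does censor early deaths on Day 1. The documents do not support that as a statement of intent: the words of rows 1 and 2 allow it, and other text points the other way.

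The argument does not settle the rest. Row 8 would still have plenty of members if row 1 overrode it, or if row 2 overrode it after one missed scan, so the empty-row reasoning says nothing about those cases.

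It is also fair to say that this SAP is written for the protocol dated 16 March 2018 and for Part 1. There, PFS only documents preliminary activity, Kaplan-Meier is optional, and no hypothesis or decision rule uses PFS. That limits the weight but does not resolve the overlap.

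**Conclusion.** Table 3 gives some deaths two opposite outcomes and no rule for choosing between them. Counting the deaths is the reading that agrees with the PFS definition. The literal reading of rows 1 and 2 contradicts that definition and biases PFS upward.

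On assumed counts, 1 to 6 deaths before any scan among about 36 Part 1 participants separate the two readings by about 3 to 17 points at Week 8. The row 1 overlap is not sized, since nothing indicates how many baselines would be inadequate.

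DOSD inherits the rules. If it is computed only in participants with a stable scan, which SAP 6.1 does not say, only the row 1 overlap can reach it. For duration of response the row 2 overlap exists only on paper, because a responder has an on-study scan.

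The weight is modest for Part 1. It would be larger if the table were used for Part 2, where protocol 2.2 makes PFS a secondary endpoint and protocol 9.4 commits to Kaplan-Meier and leaves the details to the SAP. The n = 30 figures describe that possible reuse, not the scope of the present SAP.

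**What to change.** Make one of two equivalent changes to Table 3:

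- limit rows 1 and 2 to participants with no death that qualifies under row 7 or row 8; or
- add a footnote that rows 7 and 8 take precedence over rows 1 and 2.

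In either case, state that row 9 still applies after two or more missed assessments and that the 28-day limit in footnote 2 is unchanged. A blanket rule that every death is an event would go too far, because it would contradict row 9 and override footnote 2. Table 4 needs no change, since deaths are censored there anyway.

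The cost is SAP wording only. PFS may look slightly less favourable. The change should be made before the analysis, and before the table is reused for Part 2.

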9.4. Efficacy Analysis

In this First-In-Patient study anti-tumor activity is a secondary CCI objective. The main analysis populations will be based on mITT and EP (see Section [Analysis Sets](#)).

Disease response will be presented in the form of participant data listings that include, but are not limited to starting dose, disease response at each visit, and best overall response. In addition, progression date, death date, date of first response and last disease assessment date, and date of last contact will be listed.

Summary of objective response rates (ORR) and clinical benefit rate (CBR) will be provided by descriptive statistics.

Progression -free survival (PFS) is the time from start date to date of first documentation of progression, or death due to any cause. Progression is defined as the appearance of local, regional or distant disease of the same type after complete response or progression of pre-existing lesions. It does not include second primary malignancies of unrelated types.

Overall survival (OS) is the time from start date to date of death due to any cause.

Duration of Response (DOR) is defined as the duration of overall response measured from the time measurement criteria are met for complete response (CR) or partial response (PR) (whichever is first recorded) until the first date that recurrent or progressive disease is objectively documented (taking as reference for progressive disease the smallest measurements recorded since the treatment started).

Duration of Stable Disease (DOSD) is defined as stable disease measured from the start of the treatment until the criteria for progression are met, taking as reference the smallest measurements recorded since the treatment started, including the baseline measurements.

Clinical Benefit Rate (CBR) is defined as the proportion of participants who achieved anti-tumor responses of Complete Response (CR), Partial Response (PR), or Stable Disease for > 6 months (SD).

The Kaplan--Meier methods will be used to analyze all time to event endpoints. Details of these endpoint analyses methods will be included in the Statistical Analysis Plan.

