2. Best overall response, by cohort, across all available tumor assessments from both treatment period and maintenance period, separately for RECIST 1.1 and irRECIST. Best overall response will be derived programmatically. In the tabular data presentation, a row of CR+PR will be added to show the results of ORR. With RECIST 1.1, tumor response (CR or PR) confirmation is optional as response rate is not the primary endpoint of the study, hence unconfirmed best overall response will be derived and presented. With irRECIST, tumor response (irCR or irPR) and disease progression (irPD) are required to be confirmed, however in this study tumor response confirmation is not required, therefore unconfirmed best overall response will be derived and presented. Descriptive statistics (frequency and percentage) will be provided.

In the “unconfirmed” analyses (ie, tumor response or progression without confirmation required), all tumor assessments data will be included for analyses. Specifically, regardless if a patient’s tumor response or progression is subsequently confirmed or not, the patient data will all be included in the “unconfirmed” analyses. This is a more comprehensive analysis where tumor confirmation is not required and not taken into account. For example in the ORR analysis, if a patient achieved CR or PR, regardless it is subsequently confirmed or not, the patient will be included in the numerator.

Additional summary combining data across different cohorts may be generated if deemed necessary. Swimmer plots will be used to display duration of treatment and tumor response at each applicable time point. Waterfall plot for individual tumor size percent change from baseline, and spider plot for individual tumor size percent change from baseline over time will be presented. These plots will be presented for RECIST 1.1 and irRECIST separately.

For all time-to-event endpoints, the Kaplan-Meier analysis may be performed if deemed necessary at the time of data analysis. If the Kaplan-Meier analysis is performed for progression-free survival, an event is defined as the first occurrence of “PD” status by investigator or death, whichever comes first, under RECIST; and is defined as the first occurrence of “irPD” status that has been subsequently confirmed or death, whichever comes first, under irRECIST. Time zero for all time-to-event analyses will be defined as the first vaccination on Cycle 1 Day 1. **CCI**

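### SAP Table 3 leaves out most progressions and deaths more than 28 days after stopping treatment, which contradicts the PFS definition in protocol 9.4 and SAP 6.1

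*SAP*

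**What the plan says.** Protocol section 9.4 says that PFS "is the time from start date to date of first documentation of progression, or death due to any cause". SAP section 6.1 repeats this, and for a Kaplan-Meier analysis defines the event as the first PD "status by investigator or death, whichever comes first, under RECIST". Neither text mentions treatment discontinuation.

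SAP Appendix 1, Table 3, does. Its event rows are "Progression Documented on or between scheduled tumor assessments prior to treatment discontinuation" and "Death without objective progression prior to treatment discontinuation", and footnote 2 extends both by adding "or within 28 days of discontinuation of treatment". Two rows censor participants who stop: "Treatment discontinuation due to toxicity or other reason" and "Treatment discontinuation for undocumented progression". In both, the censoring date is the last objective tumor assessment before stopping, or within 28 days of it by the same footnote. One row has no such limit: "Death prior to first planned tumor assessment" is an event on the date of death, whatever the treatment status. The closing note to the appendix applies the PFS censoring rules to DOR and DOSD.

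Section 2 of the SAP says that it takes precedence over the protocol's statistical text and will point out substantial differences. This difference is not pointed out.

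**The concern.** Two programmers, one working from SAP 6.1 and one from Table 3, would obtain different PFS results from the same data.

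The censoring may also be informative. Kaplan-Meier assumes that those censored have the same future risk as those still followed. That is hard to defend for participants who stop because they are thought to be progressing without a scan to show it. It is less clear for those who stop for toxicity.

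The information left out is partly collected anyway. Protocol section 6.5 follows survival every 3 months after stopping, and the RECIST appendices of both documents ask sites to try to document progression after treatment ends. Part 2 is a single cohort of about 30 with no control arm, so any distortion falls directly on the reported estimate.

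**Working it through.** The documents give no expected median PFS, event count or discontinuation rate, so there is no planned figure to reproduce. The check has three steps.

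**1. The rules side by side**

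| Participant | Protocol 9.4 and SAP 6.1 | SAP Table 3 |
|---|---|---|
| Stops, progression or death within 28 days | Event | Event |
| Stops, documented progression after 28 days | Event | Censored at last scan before stopping or within 28 days of it |
| Stops, dies after 28 days but before first planned scan (week 8) | Event | Event |
| Stops, dies after 28 days and after first planned scan | Event | Censored as in the second row |

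Table 3 has no row that names the late events. Their exclusion follows because the event rows end at 28 days and the discontinuation rows then assign the outcome.

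**2. A 30-participant example (invented data)**

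Documented progressions: 6, 5, 4 and 3 on days 56, 112, 168 and 224. Three participants are censored on day 308. Nine stop on day 60 without documented progression, with their last scan on day 56. Survival is the product of (1 - events / at risk), and 24 weeks is day 168.

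- Table 3 (the nine censored on day 56): 24/30 × 10/15 × 6/10 = 0.32. Median 168 days.
- Stated definition, the nine die on day 100: 24/30 × 15/24 × 10/15 × 6/10 = 0.20. Median 100 days.
- Stated definition, the nine have their event on day 300: 24/30 × 19/24 × 15/19 = 0.50. Median 168 days.

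The same Table 3 result is too high in one case and too low in the other.

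**3. Simulation, 200,000 participants per scenario**

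From the protocol: scans every 8 weeks to week 32, then every 12 weeks, with an end-of-treatment scan if more than 6 weeks have passed since the last one. Assumed, not in the documents:

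- On-treatment PFS events are exponential with median 120 days: hazard = ln 2 / 120 = 0.00578 per day.
- 30% stop before an event: stopping hazard = 0.00578 × 0.30 / 0.70 = 0.00248 per day.
- After stopping, the event hazard is multiplied by a ratio HR.
- 20% of first events are deaths, dated exactly. Progressions are dated at the next scan, and for the stated definition scans are assumed to continue after stopping.

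| HR after stopping | 24-week PFS, stated definition | 24-week PFS, Table 3 | Shift | PFS events dropped |
|---|---|---|---|---|
| 0.5 | 0.417 | 0.372 | -0.045 | 28.9% |
| 1 | 0.380 | 0.370 | -0.010 | 28.3% |
| 1.5 | 0.351 | 0.366 | +0.015 | 27.5% |
| 2 | 0.332 | 0.363 | +0.031 | 26.6% |
| 3 | 0.304 | 0.355 | +0.051 | 25.4% |

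Range of the shift over HR 0.5 to 3 under other assumptions:

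- 15% stopping: -0.021 to +0.022.
- 45% stopping: -0.079 to +0.079.
- Median 84 days, 30% stopping: -0.061 to +0.048.
- Median 180 days, 30% stopping: -0.027 to +0.041.

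The coding of the censoring date also matters. With censoring at the last scheduled scan before stopping and no end-of-treatment scan, the base case (120 days, 30%) runs from 0.350 - 0.417 = -0.067 to 0.337 - 0.304 = +0.033. Moving the censoring date further back discards event-free time and lowers the Table 3 curve.

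**The case against.** The strongest reply is that this is a text mismatch in an analysis of limited weight. The SAP is written for the protocol of 16 March 2018 and Part 1, and it makes Kaplan-Meier analysis optional. In Part 2, PFS and DOR are secondary, and no test, sample size or decision rule uses them. With 30 participants and a true 24-week PFS of 0.380, the standard error ignoring censoring is √(0.380 × 0.620 / 30) = 0.089, larger than any shift in the base table.

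The effect should also be limited by the protocol itself. Participants are encouraged to stay on treatment for at least 24 weeks despite progression, so many first progressions will be documented before stopping, and the end-of-treatment scan catches others. Because scheduled imaging ends at permanent discontinuation, the stated definition has its own weakness: some participants will be dated at death, later than a progression nobody saw.

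All of this stands, and it limits the priority of the point. It does not remove the contradiction. Protocol 9.4 says that Kaplan-Meier will be used for all time-to-event endpoints and leaves the details to the SAP, and Table 3 is the only PFS censoring rule in the documents supplied. A systematic shift smaller than one standard error is still a shift that the reader of a single-arm result cannot see.

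**Conclusion.** Table 3 and the PFS definition in protocol 9.4 and SAP 6.1 are incompatible for participants who stop treatment without documented progression and have an event more than 28 days later. The one exception is death before the first planned assessment. This rests on the text alone.

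The censoring is potentially informative. An upward shift is probable where stopping signals clinical failure, most clearly for undocumented progression. Under the base assumptions (median 120 days, 30% stopping first), 24-week PFS moves by -0.045 to +0.051 for hazard ratios of 0.5 to 3. These figures illustrate the possible size and are not estimates for this trial.

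Three stronger readings are tempting and not supported:

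- A reader might infer that PFS is biased upward. The documents do not give the risk after stopping, and the sign reverses when that risk is low, as it could be for toxicity stops in participants who are benefiting.
- A reader might infer that every event after 28 days is lost, or that censoring falls on the stopping date. The early-death row contradicts the first, and the last-assessment rule contradicts the second.
- A reader might infer that the Part 2 primary result is affected. The primary efficacy endpoint is CBR, a proportion, and Table 3 is not stated to govern it.

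**What to change.** In Table 3, count every documented RECIST 1.1 progression and every death as a PFS event regardless of treatment discontinuation, in line with protocol 9.4 and SAP 6.1. With that:

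- State that the rule for two or more missed assessments applies only to scans that were scheduled. Scheduled imaging stops at discontinuation, so otherwise the rule could censor again the late deaths that the change recovers.
- State one explicit rule for new anticancer therapy. Table 3 has none, and the row in Table 4 covers only therapy started less than 28 days after stopping.
- Say how the revised rules apply to DOR and DOSD. Their definitions in protocol 9.4 end at progression and do not mention death.
- Keep the present Table 3 rule as a sensitivity analysis, and report the number censored at discontinuation by reason.

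The cost is SAP wording and one extra analysis run, with no new data collection. The downside is the late dating of some events after imaging ends. Showing both analyses makes that visible.
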